Subsequent weekly Study Drug administrations from Weeks 2 to 5 will be self-administered by the subject or administered by an adequately trained caregiver as an outpatient SC administration. A visiting study nurse will assess and record compliance with Study Drug administration at the subject's home as well as provide guidance and training on Study Drug administration as needed. At Week 6/End-of-Trial, Study Drug may be self-administered or administered at the Study site/clinic.

Investigators are encouraged to schedule subjects at the Study Site/Clinic for an in-person Interval Evaluation Visit during approximately Weeks 3-4 to assist the Investigator in the clinical management of the subject. However, this visit is not mandatory, and therefore not all subjects will have this visit.

Subjects reporting worsening of pericarditis symptoms or AEs may be brought in for an unscheduled visit at the Study Site/Clinic at any time during the Treatment Period, at the discretion of the Investigator. Any subject who is considered by the Investigator to be a "Treatment Failure" may be withdrawn from further Study Drug treatment at the discretion of the Investigator and receive rescue therapy for their pericarditis according to standard of care as per Investigator decision; these subjects will be followed for safety for the remainder of the 6- week Treatment Period. Subjects identified as "Treatment Failures" may be replaced at the discretion of the Sponsor in order to provide an adequate sampling of subjects completing the active Treatment Period.

During the Treatment Period, subjects will continue documentation of pericarditis treatment medication use as well as rescue (pain) medication use in the medication diary. Subject-reported pericardial pain evaluations will be performed on-site at the Study Site/Clinic and by weekly (and on Day 3) Investigator (or designee) telephone calls/virtual visits using a validated 11-point NRS instrument. A subject-reported QoL questionnaire will be administered at Visit 7 (Study Site/Clinic). Weekly blood samples for central laboratory

testing will be collected at the Study Site/Clinic or at a qualified laboratory site in the vicinity of the subject or by a visiting study nurse.

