#### **5.4.9.8. Prednisone Use**

The following characteristics of prednisone use throughout the study will be summarized descriptively. Prednisone use will be identified via medical review of baseline and concomitant medications.

- Daily dose of prednisone at study baseline (mg/day) in subjects who were treated with study drug in TP and who were taking prednisone at baseline
- Daily dose of prednisone at the start of extension period (mg/day) in subjects who were treated in EP with study drug and received prednisone at EP start
- For each subject with prednisone use at baseline, the subject's average daily dose in the Treatment Period (mg/day), defined as total cumulative dose of prednisone taken in the Treatment Period divided by the duration of the Treatment Period in days. For the purposes of this analysis the Treatment Period ends on the day of Week 6/End of Trial/Visit 7 for subjects who proceed to the Extension Period; for subjects who do not enter the Extension Period, the Treatment Period ends on the day of the last study drug dose.
- For each subject with prednisone use at the start of the extension period, the subject's average daily dose in the Extension Period (mg/day), defined as total cumulative dose of prednisone taken in the Extension Period divided by the duration of treatment in the Extension Period in days. For the purposes of this analysis the Extension Period starts on the day of Week 6/End of Trial/Visit 7.
- For each subject with prednisone use at baseline, the subject's average daily dose in the Treatment and Extension Periods combined (mg/day), defined as total cumulative dose of prednisone taken in both the Treatment and Extension Periods

divided by the duration of periods in days (from the first dose in the Treatment Period to the last dose in the Extension Period).

This analysis will be performed by study part, but also for pooled groups of Parts 1, 2 and 4 and Parts 3 and 5.

To evaluate disease activity after discontinuation of corticosteroids, selected efficacy parameters including CRP will be analysed in subjects who received prednisone at baseline and discontinued it by the end of EP.

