#### **5.4.9.9. Concomitant Pericarditis Medications**

Pericarditis medications will be identified among subjects' concomitant medications and classified as analgesics, aspirin, NSAIDs, colchicine or corticosteroids through medical review.

For the purposes of these analyses, medications taken on as needed basis (PRN) will not be accounted for due to difficulty in assessing the actual dose. Only medications with a fixed daily use frequency (QD, BID, TID, etc.) will be used, so that their daily dose can be calculated.

For the purposes of these analyses, the Treatment period ends and the Extension Period starts on the day of Visit 7 for subjects who proceed to the Extension Period. For subjects who do not enter the Extension Period, the Treatment Period ends on the day of the last study drug dose.

Each category of pericarditis medications will be analyzed for changes in the Treatment Period, Extension Period and the study as a whole as follows and categorized as follows:

1. New Medication: a new medication of the given category is taken at the end of the period compared to the start of the period.
2. Dose Increase: no new medications of the given category are taken, but the total daily dose of one of the medications increased by the end of the period compared to the start of the period.
3. Dose Decrease: there are no new medications and no dose increases, and the total daily dose of one of the medications decreased by the end of the period compared to the start of the period.
4. Stopped: a medication of the given category was taken at the start of the period, and none is taken at the end of the period.
5. Stable Dosing: none of the above.

Number and percentage of subjects with each of the above outcomes will be presented by the pericarditis medication category and study period (Treatment, Extension and study as a whole). The population will be mITT for the Treatment Period and EP for the Extension

Period and the study as a whole. The denominator for percentages for the “New Medication” outcome will be the total number of subjects in the appropriate population. For all other outcomes it will be the number of subjects who take any medication of the given category at the start of the period.

This analysis will be performed by study part, but also for pooled groups of Parts 1, 2 and 4 and Parts 3 and 5.

Use of Pain/Rescue medications will be also analysed (see section 5.4.10.7).

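### The medication analyses end the Treatment Period at the last dose for subjects who do not enter the Extension, so corticosteroids started or raised after that dose reach no medication-change table

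*SAP*

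**What the plan says.** Two SAP sections define the Treatment Period for medication use.

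- Section 5.4.9.8 (prednisone): "the Treatment Period ends on the day of Week 6/End of Trial/Visit 7 for subjects who proceed to the Extension Period", whereas "for subjects who do not enter the Extension Period, the Treatment Period ends on the day of the last study drug dose". The average daily dose for the period, in subjects on prednisone at baseline, is the cumulative dose divided by the length of this period.
- Section 5.4.9.9 (all pericarditis medication categories) repeats the split: "For subjects who do not enter the Extension Period, the Treatment Period ends on the day of the last study drug dose". Each subject is classified by comparing the end of the period with its start, for example "New Medication: a new medication of the given category is taken at the end of the period compared to the start of the period".

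On populations, Section 5.4.9.9 says "The population will be mITT for the Treatment Period and EP for the Extension" Period; the same sentence gives the study as a whole the EP population too. Section 5.2.4 limits that population to subjects dosed in the Extension.

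The combined prednisone average in Section 5.4.9.8 covers every baseline prednisone user but runs "from the first dose in the Treatment Period to the last dose in the Extension Period".

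Section 2.2 lets a Treatment Failure stop study drug and receive rescue therapy, and adds "these subjects will be followed for safety for the remainder of the 6- week Treatment Period". It also says "At Week 6/End-of-Trial, Study Drug may be self-administered or administered at the Study site/clinic", without limiting that dose to any subgroup. Footnote f of the schedule (Section 8.1) does limit it: a Visit 7 dose is given only to subjects continuing into the Extension.

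**The concern.** One named period in one table has two different ends, and which end applies depends on something decided after baseline. Section 2.2 offers the Extension to responders at the investigator's discretion. The shorter window therefore falls mainly on non-responders, together with responders who decline or are not offered the Extension.

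The days cut off are the ones on which rescue treatment is most likely to begin. A subject who fails, stops study drug and then has a corticosteroid started or increased is classified by the position on the last dose day. That subject can appear as Stable Dosing instead of Dose Increase, or is not counted under New Medication while remaining in its mITT denominator. If the subject was on prednisone at baseline, the Treatment Period average omits the higher dose as well. The tables would then understate steroid escalation in the subjects who did worst on study drug.

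**Working it through.** **Which dose is last.** Table 1 puts Doses 1 to 6 at Visits 1 to 6. Section 5.2.3 counts 6 doses, the first being two injections, so planned Treatment Period injections are 6 + 1 = 7. That reproduces the figure of 7 in Section 5.4.8. It agrees with footnote f: the Visit 7 dose belongs to the Extension, and a non-entrant completer's last dose is Dose 6 at Visit 6.

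**Nominal days** (protocol numbering, first dose = day 0; the SAP's study day is one higher). With weekly dosing, Dose k falls on day 7(k − 1), so Dose 6 is on day 35. Table 1 labels both Visit 6 and Visit 7 as Week 6, but its other anchors place Visit 7 at Week 7: 15 − 8 = 7 and 20 − 13 = 7 (footnote t), and 25 − 18 = 7 (final visit). Week 7 starts on day 42. Footnote c allows ±1 day per interval, so Visit 6 to Visit 7 is 6 to 8 days.

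**Days not counted for a non-entrant.** An entrant's period runs from day 0 to day 42, which is 43 days inclusive. For last dose day d, days counted = d + 1 and days not counted = 42 − d.

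| Last dose | Day d | Counted | Not counted | Share of 43 |
|---|---|---|---|---|
| Dose 6 (completer) | 35 | 36 | 7 | 16.3% |
| Dose 5 | 28 | 29 | 14 | 32.6% |
| Dose 4 | 21 | 22 | 21 | 48.8% |
| Dose 3 | 14 | 15 | 28 | 65.1% |
| Dose 2 | 7 | 8 | 35 | 81.4% |
| Dose 1 | 0 | 1 | 42 | 97.7% |

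After a single dose, start and end fall on the same day and no change can be recorded.

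**Whether another change table recovers these days.** The Extension and whole-study tables require an Extension dose, so a non-entrant is in neither. The combined prednisone average needs a last Extension dose, which a non-entrant does not have, so its end date is undefined for that subject.

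**Effect on the prednisone average.** The doses are assumed, not taken from the SAP: 10 mg/day at baseline, raised to 20 or 40 mg/day on the day after the last study drug dose. Average to day 42 = [10(d + 1) + r(42 − d)] / 43, where r is the raised dose.

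- Completer: (360 + 140)/43 = 11.6; (360 + 280)/43 = 14.9 mg/day.
- Last dose Dose 3: (150 + 560)/43 = 16.5; (150 + 1120)/43 = 29.5 mg/day.
- Last dose Dose 2: (80 + 700)/43 = 18.1; (80 + 1400)/43 = 34.4 mg/day.

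Under the SAP rule the reported figure is 10.0 mg/day in every case.

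**Effect on a percentage.** One missed New Medication is 1/40 = 2.5 percentage points if all 40 planned subjects formed a single group, and more within a Part or pooled group.

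**The case against.** The best defence is that this is a deliberate on-treatment window. Both sections present it as specific to these analyses, it can be programmed as written, and the weaning objective for Parts 3 and 5 concerns weaning during KPL-914 treatment. Steroids begun after study drug is stopped answer a different question.

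That would justify some on-treatment rule, but not this one. Entrants are counted through the week after Dose 6, while completers who do not enter are cut off on the day of Dose 6, although the same weekly dose covers the same week. An on-treatment window would need one rule for both groups.

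Three stronger readings are tempting but not supported:

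- That the rule contradicts Section 2.2. Failures are followed there for safety, and an analysis-specific window can coexist with safety follow-up. The two are in tension, no more.
- That the primary objective of Parts 3 and 5 is compromised. Section 2.2 encourages tapering in the Extension, and the last paragraph of Section 5.4.9.8 looks at subjects who came off prednisone by the end of the Extension. The link is indirect.
- That rescue steroids vanish from the report. They still enter the concomitant medication summary and listing (Section 5.4.6), and possibly the other category in Section 5.4.10.7, depending on the eCRF. Discontinuation reasons (Section 5.4.1) and recurrences (Section 5.4.9.10) are also tabulated. What is missing is the change in medication.

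Two limits also stand. A steroid started by the last dose day and still taken then is counted. A subject newly started on prednisone is outside the Treatment Period average under any window, because that average covers baseline users only.

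**Conclusion.** The point holds as a minor defect in two descriptive analyses. The period ends differ by 7 days (6 to 8) for completers who do not enter the Extension, and by 14 to 42 days for subjects stopped after Doses 5 to 1. Corticosteroids started or increased in that gap are in no medication-change table, and for baseline prednisone users they are outside the Treatment Period average. The combined average has no defined end for non-entrants.

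The day counts rest on nominal weekly visits and on footnote f being followed. If non-entrants were in fact dosed at Visit 7, as the unrestricted sentence in Section 2.2 might suggest, the gap for completers would close but the gap for early stoppers would remain. The mg/day figures are illustrative. The SAP gives neither the number of non-entrants nor the allocation to Parts, so the effect on any one table cannot be stated. Compliance, Per-Protocol membership and the by-visit CRP and pain results are not touched, and no inferential result depends on this.

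**What to change.** In Sections 5.4.9.8 and 5.4.9.9:

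- End the Treatment Period for every treated subject at the scheduled Week 6/End-of-Trial Visit 7. If there is none, end it at nominal day 42 or study exit, whichever is first.
- State that End-of-Trial procedures done early at discontinuation do not count as Visit 7. Footnote b asks early discontinuers to complete these procedures without saying when, so without this sentence the window could still close soon after the last dose.
- Use the mITT population for the whole-study medication-change table.
- End the combined prednisone average for non-entrants at their Treatment Period end.
- If an on-treatment view is wanted, add it as a second summary with one rule for entrants and non-entrants, for example last Treatment Period dose plus 7 days.

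Bringing the Week 6 dosing sentence in Section 2.2 into line with footnote f would remove the doubt about which dose is last.

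The cost is a few sentences and one derivation rule. The downside is that, for early discontinuers, the tables will include steroid use after study drug was stopped. They can do so only as far as the recorded medication data reach; whether dose-level data run to day 42 for these subjects depends on the protocol and eCRF, which are not at hand.

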**Extension Period (EP):** The EP is defined as the 18 weeks following the Treatment Period. Subjects who are considered to be “Treatment Responders” will be, at the discretion of the Investigator, offered participation in an optional 18-week EP, in which weekly administration of open-label KPL-914 may be continued for a total duration of 24 weeks. The weekly KPL-914 doses will be by self-administration or administered by adequately trained caregiver, and study nurse visits to the subject’s home as well as Investigator (or designee) telephone calls/virtual visits will continue on a monthly basis. During the EP, the Investigator is encouraged to wean concomitant NSAIDs, and/or colchicine, and/or corticosteroids. It is encouraged that NSAIDs and colchicine be tapered and withdrawn within 15 days after entry into the EP. It is encouraged that corticosteroids be progressively tapered (e.g., by 5 mg prednisone or equivalent every week in adults or 0.2mg/kg every week in subjects <18yo) and discontinued within 6 weeks after entering to EP (i.e., by Study Week 12) unless in the opinion of Investigator, a different corticosteroid weaning schedule is required based on subject’s clinical status. Other pericarditis medications may also be initiated at the discretion of the Investigator. All changes to pericarditis-related medications should be captured in the source records and eCRF

Unscheduled clinic visits can be scheduled any time as determined by the Investigator/upon subject request. In addition, Investigators are encouraged to schedule subjects at the Study Site/Clinic for an in-person Interval Evaluation Visit between Weeks 15 to 20 (8 to 13 weeks after Visit 7) to assist the Investigator in the clinical management of the subject. During this visit a physical examination, vital signs, ECG, echocardiogram, and laboratory testing can be performed. However, this visit is not mandatory, and therefore not all subjects will have it.

Subject-reported pericardial pain evaluations using a validated 11-point NRS instrument as well as AE monitoring will be performed during the EP at on-site clinic visits and/or during monthly Investigator (or designee) phone calls/virtual visits. A subject-reported QoL questionnaire will be administered at the Interval Evaluation Visit and the Final Visit of the EP. At the end of the EP, subjects will complete the Week 25/Final Visit.

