### **5. STATISTICAL METHODOLOGY**

#### **5.1. General Considerations**

All statistical evaluations will be conducted using SAS® version 9.4 or higher (SAS® Institute, Cary, North Carolina). All tables, figures and listings will be produced in landscape format.

Because of the small sample size no inferential statistical analyses or hierarchical testing are planned. Analysis will be descriptive in nature.

Each Part will be analyzed separately. Tables will have columns corresponding to or be stratified by study Parts. Select analyses, as specified in further sections, will be performed for pooled groups of Parts 1, 2 and 4 and Parts 3 and 5, representing similar RIP and PPS populations, i.e. symptomatic and asymptomatic-CS dependent subjects. In general, all data will be listed by study part, subject and visit/time point where appropriate. The total number of subjects under the stated population (N) will be displayed in the header of summary tables.

Data will be summarized using descriptive statistics for continuous variables. Unless otherwise specified, descriptive statistics will include number of subjects, mean, standard deviation, minimum, median and maximum. In case of  $n < 2$ , where  $n$  indicates the number of evaluable subjects at the particular time point, the standard deviation will not be calculated.. The statistic “Missing” will also be presented as the number of missing entries/subjects, if any

at that visit/timepoint, and presented as a summary statistic only when non-zero. The minimum and maximum statistics will be presented to the same number of decimal places as the original data. The mean and median will be presented to one more decimal place than the original data, whereas the standard deviation will be presented to two more decimal places than the original data.

In summary tables of categorical variables, counts and percentages will be used. The count [n] indicates the actual number of subjects with a particular value of a variable or event, which should always be less than or equal to the total number of subjects with non-missing value of the variable or event [M]. Percentage will be obtained by:  $\% = (n/M)*100$ . Unless otherwise stated, all percentages will be expressed to one decimal place.

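### SAP 5.4.9.9 counts non-users of a drug class as Stable Dosing over a denominator of users only; secondarily, it cannot separate a within-class switch from an add-on or first use

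*SAP*

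**What the plan says.** Section 5.4.9.9 takes the concomitant pericarditis drugs, "classified as analgesics, aspirin, NSAIDs, colchicine or corticosteroids through medical review", and compares the end of each period with its start within each class. As-needed use is ignored. The outcomes are:

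- Item 1 reads "New Medication: a new medication of the given category is taken at the end of the period compared to the start of the period".
- Item 2 (Dose Increase) applies if the class contains no added product and "the total daily dose of one of the medications increased by the end of the period".
- Item 3 (Dose Decrease) applies if "there are no new medications and no dose increases, and the total daily dose of one of the medications decreased".
- Item 4 (Stopped) applies to a subject with some product of the class at the start and none at the end.
- Item 5 reads "Stable Dosing: none of the above".

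The percentage for New Medication uses the whole population (mITT or Extension Period). For every other outcome the denominator is different: "it will be the number of subjects who take any medication of the given category at the start of the period".

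Section 5.1 sets the general rule for categorical tables. It defines the count as the subjects with a given value, "which should always be less than or equal to the total number of subjects with non-missing value of the variable or event".

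**The concern.** Item 5 carries no condition that the subject uses the class at all, while its denominator does. The numerator and denominator of one row therefore refer to different sets of subjects. A programmer who follows the text gets a Stable Dosing percentage that grows with the number of non-users, and non-use says nothing about stability of dosing.

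The second issue is the unit of comparison. Item 1 is triggered by any product present at the end and absent at the start, and it blocks items 2 and 3, which themselves look at the dose of one product. No class total is compared. In a class with several products, replacing one by another gets the same label as adding a second product or starting the class for the first time. For corticosteroids this matters because feasibility of weaning is the primary objective of Parts 3 and 5, and section 2.2 itself describes the taper across products: "by 5 mg prednisone or equivalent every week in adults".

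**Working it through.** The plan gives no figure for this table and no counts of users, so there is nothing to reproduce. The check applies the five rules literally to each start/end pattern and then works through the percentages with assumed counts.

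**Literal classification**

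| Pattern (start to end) | Outcome | In users-at-start denominator? |
|---|---|---|
| None to none | Stable Dosing | No |
| A to A, same dose | Stable Dosing | Yes |
| A to B | New Medication | Yes |
| A to B, lower equivalent dose | New Medication | Yes |
| A to A plus B | New Medication | Yes |
| None to A | New Medication | No |

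The first row is the conflict between numerator and denominator. The last four rows are four clinical situations under one label.

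**Size of the Stable Dosing error**

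Let u be users at the start, s the users who are unchanged, and v the subjects with none of the class at start or end.

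- Literal text: (s + v)/u.
- Users only: s/u.
- Inflation: v/u, above zero whenever v > 0.
- The literal figure exceeds 100% when s + v > u, that is, when v > u − s: non-users outnumber the users who changed.

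Illustration, all counts assumed: 30 subjects, u = 12, of whom 7 stop and s = 5 are unchanged; v = 30 − 12 = 18.

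- Literal: (5 + 18)/12 = 23/12 = 192%.
- Users only: 5/12 = 42%.

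Range, using the planned total of about 40 subjects (section 3.1), assuming that half of the users are unchanged and that no non-user starts the class:

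| u | Literal | Users only |
|---|---|---|
| 10 | 35/10 = 350.0% | 50.0% |
| 20 | 30/20 = 150.0% | 50.0% |
| 30 | 25/30 = 83.3% | 50.0% |
| 36 | 22/36 = 61.1% | 50.0% |

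The last two rows matter most in practice: the figure is wrong but looks plausible.

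**Size of the switch effect**

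Take again 12 users among 30 subjects (assumed), and one user who ends the period on a different product at a lower equivalent dose.

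- Dose Decrease loses 1/12 = 8.3 percentage points, because the subject leaves the numerator and stays in the denominator.
- New Medication gains 1/30 = 3.3 points, because its denominator is the whole population.

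**The case against.** The best defence on Stable Dosing is that the plan can be read sensibly. The denominator is users at the start, section 5.1 forbids a count above its denominator, and the word dosing presupposes a dose. Read together, these suggest that only users were meant, and a percentage above 100% would be noticed. This makes the intent fairly clear, but item 5 does not state it. An inflated value below 100% would not be noticed.

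On switching, comparing products is defensible for NSAIDs and analgesics, since milligrams of different products cannot be added. That stands, and it is why the remedy for those classes should be separate rows and not a class total.

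A reader might infer that a taper passing through a second steroid is shown as escalation. The text does not support this. The rules compare only the start and end of a period, so a subject off steroids by the end is Stopped, whatever came between. Section 2.2 encourages corticosteroid discontinuation by Study Week 12, and the final visit is at Week 25, so a taper completed on that schedule is unaffected over the Extension Period and over the study as a whole. Nor does the plan call New Medication an escalation.

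A reader might also infer that the weaning objective depends on this table. It does not: the primary endpoint of Parts 3 and 5 is disease activity after taper, and section 5.4.9.8 summarises daily prednisone dose by period. That section covers prednisone only, however, so it does not repair the corticosteroid row here.

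**Conclusion.** The Stable Dosing row is defective as written: its residual numerator includes subjects whom its denominator excludes. The bias is always upward and equals the number of subjects with none of the class at start or end, divided by the users at the start. The 192% against 42% is an illustration with assumed counts; the document gives none. Parts 3 and 5 enrol corticosteroid-dependent subjects, so for that class the problem falls mainly on Parts 1, 2 and 4 and on extension periods that begin after an earlier stop. It also applies to the other drug classes.

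The switch point is secondary. It concerns only classes with several products (corticosteroids, NSAIDs, analgesics) and only subjects still on a different product at period end. The 8.3-point loss applies to Dose Decrease and only where the equivalent dose fell; it is not the shift in New Medication, which is 3.3 points under the same assumptions.

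All of this concerns descriptive tables. No test, error rate or sample size is affected.

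**What to change.** 1. Reword item 5 so that Stable Dosing covers subjects who take the class at the start of the period and meet none of items 1 to 4. The percentage then cannot exceed 100%. This costs one clause.
2. For corticosteroids, classify on total daily class dose in prednisone equivalents, with the conversion factors fixed in advance. A switch is then read as a rise, a fall or no change in class dose.
3. For the other classes, report separately (a) first use of the class, (b) a product added to one that continues, and (c) a switch, meaning a new product with the earlier one stopped. Simply reserving New Medication for subjects with no prior use of the class would not do: a subject who adds a second NSAID at an unchanged dose of the first could then fall into Stable Dosing, and an intensification that the present rule captures would be hidden.

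No new data are needed. The costs are a conversion table agreed before the analysis and a few more rows in the output.
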